11. DEMOGRAPHIC AND OTHER BASELINE CHARACTERISTICS

Demographic data and other baseline characteristics will be presented for the ITT population, SAF population, and PP population. For the ITT and PP populations, the data will be presented by randomized treatment groups. For the SAF population, the data will be presented by the predominant treatment received.

No statistical testing will be carried out for demographic or other baseline characteristics.

The following demographic and other baseline characteristics will be reported for this study:

- Age (years) - calculated relative to date of informed consent, as a continuous variable and categorically:
 - o < 55 years
 - o \geq 55 years
 - and
 - o < 65 years
 - o \geq 65 years
 - and
 - o \leq 18 years
 - o >18 and <65 years
 - o \geq 65 years
- Gender
- Race

Document:

Author:

Version Number:

V2.0

Version Date:

21MAY2020

Template No: CS_TP_BS016 Revision 4
Effective Date: 01Apr2016

Reference: CS_WI_BS005

- American Indian or Alaska Native
 - Asian
 - Black or African American
 - Native Hawaiian or Other Pacific Islander
 - White
 - Multiracials as is (where more than one race is selected, ie, White/Asian, Black/Other)
 - Other
 - Other including multiracials
 - Non-White (Black or African American, American Indian or Alaska Native, Asian, Native Hawaiian or Other Pacific Islanders, and Other including multiracials)
- Ethnicity
 - Hispanic or Latino
 - Not Hispanic or Latino
- Country
 - Bulgaria
 - Poland
 - Russia
 - Serbia
 - Slovakia
 - Ukraine
 - USA
 - Japan
- Region
 - US
 - Europe
 - European Union (Bulgaria, Poland, Slovakia): for EudraCT
 - Japan
- Weight (kg)
- Height (cm)
- BMI (kg/m²), as a continuous variable and categorically:
 - Underweight: < 18.5
 - Normal: 18.5 to < 25.0
 - Overweight: 25.0 to < 30.0
 - Obese: >= 30.0
- Waist circumference (cm)
- Baseline MADRS total score, as a continuous variable

Document:

Author:

Version Number:

V2.0

Version Date:

21MAY2020

Template No: CS_TP_BS016 Revision 4
Effective Date: 01Apr2016

Reference: CS_WI_BS005

- Baseline CGI-BP-S depression score, as a continuous variable

Demographic data collected for all screened subjects will be listed.

The following psychiatric history data will be summarized for the SAF population in a separate table:

- Age at onset of bipolar I disorder
- Time since initial onset of bipolar I disorder, in years, calculated relative to date of informed consent (see [APPENDIX 2](#) for partial date imputation rules)
- Time since onset of current episode of major depression associated with bipolar I disorder symptoms, in months, calculated relative to date of informed consent (see [APPENDIX 2](#) for partial date imputation rules)
- Frequency distribution of number of prior hospitalizations for Bipolar I depression (0, 1, 2, 3, and 4 or more)
- Frequency distribution of DSM-5 code in ascending numeric order
- Bipolar I diagnosis subtype (Bipolar I disorder without rapid Cycling and Bipolar I disorder with rapid cycling)
- Number and percentage of subjects with other psychiatric disorders
- Number and percentage of subjects with any other psychiatric disorders

Other psychiatric Disorder data will be summarized for SAF population in a separate table by summarizing Diagnosis and DSM-5 codes.

11.1.DERIVATIONS

- Time since initial onset of bipolar disorder (years):

(Date of informed consent – date of initial onset of bipolar disorder) / 365.25

- Time since initial onset of current episode of major depression (months):

(Date of informed consent – date of initial onset of current episode of major depression) / 30.25

12. MEDICAL HISTORY

Medical History information will be presented for the ITT and the SAF populations by treatment group. Medical and surgical history information, including both past and concomitant medical conditions and major surgical history, as collected on the Medical History CRF form, will be coded using MedDRA,

Document:

Author:

Version Number:

V2.0

Version Date:

21MAY2020

Template No: CS_TP_BS016 Revision 4
Effective Date: 01Apr2016

Reference: CS_WI_BS005

Version 19.1 or higher, and presented by SOC and PT. Medical History will be sorted alphabetically by SOC and by decreasing frequency of PT in the All SEP-4199 column.

13. MEDICATIONS

Medications will be presented for the SAF population and coded to indication-specific Anatomical Therapeutic Chemical (ATC) Level 3 and PT according to World Health Organization Drug (WHODRUG) drug dictionary, Version 01MAR2017 or higher. If ATC level 3 is missing then ATC level 2 will be used. Medication will be sorted alphabetically by ATC level3 and by decreasing frequency of PT in the All SEP-4199 column.

Whenever available, the time information should be accounted for in the derivation of prior, concomitant, and post-treatment medications, see [APPENDIX 2](#) for the handling of partial dates for medications. In the case where it is not possible to define a medication as prior, concomitant, or post-treatment, the medication will be classified by the worst case; ie, concomitant.

- Prior medications are medications which stopped prior to the first dose of study drug.
- Concomitant medications are medications that:
 - Started prior to, at the time of, or after the first dose of study drug, AND
 - Started before or at the date (day) of the last dose of study drug, AND
 - Ended at the time of or after the first dose of study drug or were ongoing at the end of the study.
- Post-treatment medications are medications which started after the day of the last dose of study drug.

Prior and concomitant medication use will be summarized by treatment group by ATC Level 3 classification and PT using the SAF population. Subjects with multiple uses of a medication will be counted only once for a given drug class or PT. Number and percentage of subjects who take concomitant benzodiazepines, sedatives, or hypnotics will be summarized by visit (including follow-up visit) and overall. Prior, concomitant, and post-treatment medications will be provided in data listings.

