Subjects who meet eligibility criteria at Screening will return to the study site on Day -1 for confirmation of screening evaluations as well as completion of predose assessments. Eligible subjects (based on confirmation of study entry criteria) will be randomized and dispensed study drug at Day -1.

Per local clinical practice, subjects may be hospitalized for up to 7 days during the first week of treatment with double-blind study drug. Further need for hospitalization will require consultation with the Medical Monitor.

Subjects will self-administer the study drug on an outpatient basis once daily with or without food beginning on Day 1 (the day after the Baseline visit) and continue for 6 weeks (the last dose of study drug will be self-administered by the subject at home on the morning of Visit 6).

Subjects will be instructed to administer study drug as a single oral dose in the morning at approximately the same time each day. Clinic visits are to begin no later than 6 hours postdose, if possible.

During the baseline (Day -1) and treatment period (Days 1 to 42), subjects will have clinic visits at Days -1, 7, 14, and 28. In order to facilitate scheduling of clinic visits, a window of \pm 2 days will be allowed for each clinic visit. Subjects will have a telephone contact at Day 35 (\pm 2).

End of Treatment (EOT)/Early Termination (ET) (Day 42 [\pm 2])

Subjects will have a clinic visit at Day 42 for assessments of efficacy and safety. Subjects who discontinue the study prior to this visit will undergo the procedures and assessments for this visit at the time of discontinuation.

Follow-up Period (Day 49 [\pm 2])

All subjects who received at least one dose of study drug will have a follow-up visit for safety and tolerability assessments 7 (\pm 2) days after their last study drug dose. Assessment of potential withdrawal effects will also be made during the follow-up period.

Efficacy, Safety, and PK/PD Assessments

Efficacy will be evaluated using the MADRS, CGI-BP-S, and HAM-A. Treatment response and symptom remission will be assessed using the MADRS. Additional assessments will include evaluation of functional impairment associated with bipolar depressive symptoms using the SDS total score and symptom severity using the QIDS-SR16 total score.

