10.3.3. Concomitant Psychotropic/Antipsychotic Medications

Treatment with benztropine (up to 6 mg/day) will be permitted as needed for movement disorders. In cases where benztropine is not available or a subject has had an inadequate response or intolerance to benztropine treatment, the following medications may be used to treat acute EPS: biperiden (up to 16 mg/day) or trihexyphenidyl (up to 15 mg/day) or diphenhydramine (up to 100 mg/day). Treatment with propranolol (up to 120 mg/day) or amantadine (up to 300 mg/day) will be permitted as needed for akathisia. These allowed medications for the treatment of EPS, akathisia, and dystonia may be given in any formulation (oral, IM, or IV) as deemed appropriate by the investigator. Medications used to treat movement disorders should not be given prophylactically. Medications used for movement disorders should be tapered and discontinued prior to randomization but may be reinstated if symptoms emerge.

In situations where anticholinergic agents or sedative/hypnotic agents (or any agents that may cause sedation) are administered, these should be taken at the same time each day and should not be taken within 8 hours of scheduled assessments. In regions that do not have the specified drugs available, similar drugs at equivalent dosages will be substituted as described in the Study Reference Manual or in consultation with the Medical Monitor.

Concomitant use of sedative hypnotics is permitted during Screening and for Weeks 1-3 (through Visit 5) at the discretion of the Investigator with the following restrictions: Lorazepam is permitted at the discretion of the Investigator up to 2 mg/day for intolerable anxiety/agitation, as clinically indicated. Lorazepam should be used sparingly, when clinically required, per investigator judgment. Lorazepam (≤ 2 mg/day), eszopiclone (≤ 3 mg/day), zopiclone (≤ 7.5 mg/day), zolpidem (≤ 10 mg/day), zolpidem CR (≤ 12.5 mg/day) and temazepam (≤ 30 mg/day) may be administered at bedtime for insomnia, as needed. Hypnotic agents should be administered no more than once nightly and should not be used in combination. Continued use of the above sedative hypnotics beyond Visit 5 requires approval from the Medical Monitor.

Anxiolytics, sedatives or hypnotics should not be administered within 8 hours prior to any psychiatric assessments.

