11.6.4. Follow-up: Visit 7 (Day 49 ± 2)

All subjects will have a follow-up visit 7 days after their last study drug dose. The following study-related procedures will be performed at Visit 7; it is suggested that they be performed in the order presented below, as is possible by the site:

- Administer YMRS.
- Administer PWC.
- Administer C-SSRS (Since Last Visit version).

- Record prior and concomitant medications.
- Record adverse events.
- Perform physical examination.
- Record weight.
- Record waist circumference.
- Obtain vital signs, including orthostatic changes in blood pressure and heart rate.
- Perform 12-lead ECG.
- Collect blood sample(s) for the following clinical laboratory tests:
 - Hematology and Serum Chemistry
 - Serum prolactin
- Collect blood sample for R- and S-amisulpride PK and plasma prolactin analysis.
- Collect urine sample for urine drug screen, urinalysis, and urine β -hCG (female subjects of childbearing potential).

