15.3.6.9. Concomitant Medications

All medications will be coded to indication-specific ATC (Anatomical Therapeutic Chemical) classification (ie, ATC level 3) and PT according to the World Health Organization drug dictionary (WHO-DD) ATC classification level 3 and Preferred Term (PT) (1 Sept 2017 or more recent).

Any medications taken during the course of the study, with a start date on or after the date of the first dose of study drug and on or before the date of the last dose of study drug; or with a start date prior to, and an end date on or after, the date of the first dose of study drug, or marked as ongoing, will be considered concomitant medications. Medications that ended prior to the date of the first dose of study drug will be considered prior medications. Medications that started after the date of the last dose of study drug will not be considered concomitant, but will be considered post-treatment.

A detailed listing of prior, concomitant, and post medications taken by subjects will be provided. The number and percentage of subjects using concomitant medication will be summarized by treatment group by ATC and PT using the Safety population. Subjects with multiple uses of a medication will be counted only once for a given drug class or PT.

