Missing	Partial	Impute stop date as latest possible date (ie, last day of month if day unknown or 31st December if day and month are unknown). Then: If stop date < SEP-4199 study med start date, then pre-treatment events If stop date >= SEP-4199 study med start date, then SEP-4199 AE
Missing	Missing	Assumed SEP-4199 AE

 Document:

Author:

Version Number:

V2.0

Version Date:

21MAY2020

 Template No: CS_TP_BS016 Revision 4
 Effective Date: 01Apr2016

Reference: CS_WI_BS005

ALGORITHM FOR PRIOR / CONCOMITANT / POST-TREATMENT MEDICATIONS:

The concept of "date" below should also include time information whenever available. Time will not be imputed.

START DATE	STOP DATE	ACTION
Known	Known	
If stop date < SEP-4199 study med start date, assign as prior.
 
If stop date >= SEP-4199 study med start date and start date <= end of treatment date (date of last dose of study drug), assign as concomitant.
 
If stop date >= SEP-4199 study med start date and start date > end of treatment (date of last dose of study drug), assign as post treatment.

Known	Partial	
Impute stop date as latest possible date:
 
 • If only day unknown, impute as the earlier of (last day of the month; date of the last study visit). • If month and day unknown, impute as the earlier of (31st December; date of the last study visit). 
Then:
 
If stop date < SEP-4199 study med start date, assign as prior.
 
If stop date >= SEP-4199 study med start date and start date <= end of treatment (date of last dose of study drug), assign as concomitant.
 
If stop date >= SEP-4199 study med start date and start date > end of treatment (date of last dose of study drug), assign as post treatment.

Known	Missing	
If stop date is missing could never be assumed a prior medication.
 
If start date <= end of treatment (date of last dose of study drug), assign as concomitant.
 
If start date > end of treatment (date of last dose of study drug), assign as post treatment.

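### The by-visit table of benzodiazepine, sedative and hypnotic use has a follow-up column, but the SAP's definition of concomitant keeps drugs started after the last-dose day out of it

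*SAP*

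**What the plan says.** SAP section 13 (Medications) sets the table: "Number and percentage of subjects who take concomitant benzodiazepines, sedatives, or hypnotics will be summarized by visit (including follow-up visit) and overall".

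The same section defines the term. One of the joint conditions for a concomitant drug is "Started before or at the date (day) of the last dose of study drug, AND". The complement is "Post-treatment medications are medications which started after the day of the last dose of study drug". Prior and concomitant use are summarised; post-treatment drugs are only listed.

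The cut is applied consistently elsewhere:

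- Protocol 15.3.6.9: "Medications that started after the date of the last dose of study drug will not be considered concomitant, but will be considered post-treatment". SAP Appendix 7, item 0.2, says the same.
- SAP Appendix 2, known start and missing stop: "If start date > end of treatment (date of last dose of study drug), assign as post treatment".

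On timing, protocol 11.6.4 says "All subjects will have a follow-up visit 7 days after their last study drug dose", and protocol 7.1 gives the window as ±2 days. Protocol 7.1 also says of that period: "Assessment of potential withdrawal effects will also be made during the follow-up period".

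**The concern.** Naming the follow-up visit in the table tells the reader that use at that visit will be shown. The definition then restricts the column to drugs carried over from treatment. Up to the last dose, the table can count both new and continuing users. After it, a drug with a known start cannot enter as new use.

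Follow-up is the off-drug week in which withdrawal effects are assessed. Adverse events are recorded until the follow-up visit (protocol 12.3), and their definition has no cut at the last dose (protocol 15.3.6.1). Insomnia with onset on Day 45 would therefore be a counted event, while a hypnotic started for it that day would be missing from the table. A reader who takes the follow-up column as all use could find a low figure more reassuring than it is. The column also gives context for the withdrawal checklist scores, since a sedative may blunt symptoms that the checklist rates.

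**Working it through.** The plan states no figure on this point, and the question involves no alpha, power or variance. The check applies the SAP's classification rule to every medication record that could arise between the last dose and follow-up.

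**Inputs**

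- First dose Day 1 and last dose Day 42 (protocol 7.1, a completer).
- Follow-up 7 (±2) days after the last dose, so Day 47, 49 or 51 at the earliest, nominal and latest.
- Rule (SAP section 13 and Appendix 2): stop before first dose = prior; otherwise start ≤ last-dose day = concomitant; otherwise start > last-dose day = post-treatment.

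**Known start after the last dose.** Let k be the number of days from the last dose to follow-up. A drug can start on any of those k days. Its stop can be any day from its start to follow-up, or be missing. The number of patterns is (k+1) + k + … + 2 = k(k+3)/2.

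| Follow-up day | k | Patterns, k(k+3)/2 | Post-treatment | Concomitant |
|---|---|---|---|---|
| 47 | 5 | 5 × 8 / 2 = 20 | 20 | 0 |
| 49 | 7 | 7 × 10 / 2 = 35 | 35 | 0 |
| 51 | 9 | 9 × 12 / 2 = 54 | 54 | 0 |

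None of these records can enter the follow-up column.

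**Records that can still enter**

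| Record | Class |
|---|---|
| Started Day 30, ongoing | Concomitant |
| Started on Day 42, the last-dose day | Concomitant |
| Start missing, stop on Day 47 | Concomitant |
| Start and stop both missing | Concomitant |

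Section 13 also sends any record that cannot be classified to concomitant. The omission is therefore complete for known starts after the last-dose day, but not for every drug first taken off study drug.

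**Is the information summarised elsewhere?** Section 13 plans summaries for prior and concomitant use only, and protocol 15.3.6.9 plans one for concomitant use only. No planned table shows post-treatment starts by arm.

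**How many subjects?** The documents give no rate of new sedative or hypnotic use after the last dose. If a share p of an arm starts one in that week, about 98p subjects are left out, using the planned 98 per arm in the US and Europe. Purely as assumptions, p = 0 gives 0, p = 3% gives 98 × 0.03 = 2.9, and p = 10% gives 98 × 0.10 = 9.8.

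**The case against.** Five points can fairly be made on the other side.

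1. **Withdrawal has its own instrument.** The Physician Withdrawal Checklist is given at end of treatment and again at follow-up. SAP 17.6.6 summarises its total score, each of the 20 symptoms, and severity. Adverse events run to follow-up. Nothing makes the sedative table a withdrawal analysis. This stands, and it limits the impact.
2. **The data source is not settled.** SAP 6.3, Table 1, lists the last dose of benzodiazepines, sedatives and hypnotics as a visit-level item separate from concomitant medication, and Appendix 7, item 0.5, uses such an item. A table built from it could show use after the last dose. Protocol 10.3 also uses the word concomitant broadly, for drugs taken between Visit 1 and Visit 7. The table templates cited in SAP section 8 are not among the documents. But section 13 does not name the visit-level item as its source, and it uses a term that it has just defined. The possible alternative source does not cure the written rule.
3. **The Week 6 to follow-up trend is not fixed.** A reader might infer that it must fall or stay flat in every arm. It need not. Someone who stops in Week 2 on ongoing lorazepam can count at follow-up without ever counting at Week 6. A completer's last dose is on the morning of Visit 6, so a hypnotic first taken that night is concomitant and can appear only at follow-up.
4. **Follow-up use need not be mostly new starts.** A reader might infer this from "Continued use of the above sedative hypnotics beyond Visit 5 requires approval from the Medical Monitor". Approval is not a ban, no approval rate is given, and subjects who leave before Visit 5 need none.
5. **A new start is not a direct sign of withdrawal.** Subjects were washed out of earlier psychotropics, so a new sedative may equally reflect relapse or a return to usual treatment.

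Points 3 to 5 rule out stronger readings. None removes the mismatch between the column's apparent scope and its definition.

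**Conclusion.** The point holds in a limited form. As the SAP is written, the follow-up column omits every benzodiazepine, sedative or hypnotic with a known start after the last-dose day, and it understates use in that week whenever such a start occurs. Starts on the last-dose day and records with a missing start date remain in.

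The extent of the omission is certain under the stated rule, but the number of subjects is unknown, and the 0 to 10% range above is illustrative only. The conclusion assumes that concomitant in the table sentence carries the meaning section 13 gives it.

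The effect is confined to one descriptive safety table. Under SAP section 17, safety data are not compared between arms unless a section says otherwise, and section 13 specifies no comparison for this table. No efficacy endpoint or confirmatory test is touched, and the omitted records stay in the listings. The documents do not support a claim that the plan hides a withdrawal effect. They support the narrower statement that this column does not show what its label suggests.

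**What to change.** In SAP section 13, for this table only:

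- count at each visit any benzodiazepine, sedative or hypnotic taken since the previous visit, whatever its start date relative to the last dose;
- include drugs classed as post-treatment in the follow-up column;
- show starts after the last dose in a separate row by arm, so that new and carried-over use can be told apart.

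If the table was meant to come from the visit-level last-dose item in SAP 6.3, the section should say so. If carried-over use alone was intended, the follow-up column should at least be labelled that way.

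The general definitions of prior, concomitant and post-treatment can stay as they are. The cost is one sentence in the SAP and a change to one table program. No new data are needed, because protocol 10.3 already records start and stop dates from Visit 1 to Visit 7.

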14. STUDY DRUG EXPOSURE

Exposure to study drug will be calculated as the number of days from first dose date to last dose date. Duration of exposure to study drug will be summarized for the SAF population.

The date of first study drug administration will be taken from the CRF "Study Drug Administration / Drug Accountability" form.

The date of last study drug will be retrieved as the latest date between "Study Drug Administration / Drug Accountability", "Blood PK Samples and 3 Prior Doses", and "Subject Disposition - End of Study" forms. For subjects who are lost to follow-up, and for whom the last dose date is unknown, the last contact date will be used.

Document:

Author:

Version Number:
Version Date:

V2.0

21MAY2020

Template No: CS_TP_BS016 Revision 4
Effective Date: 01Apr2016

Reference: CS_WI_BS005

Interruptions and compliance are not taken into account for duration of exposure.

Overall number of tablets taken will be described by treatment group and overall as a continuous variable.

Duration (in days) of exposure will be summarized both as a continuous variable and categorically, and by planned visit days:

- Number and percentage of subjects with drug exposure $\geq 4, \geq 7, \geq 14, \geq 21, \geq 28, \geq 35$, and ≥ 42 days;
- Number and percentage of subjects with drug exposure for 1 - 3, 4 - 6, 7 - 13, 14 - 20, 21 - 27, 28 - 34, 35 - 41 and ≥ 42 days.

Person years of exposure will be described by treatment group and overall.

